4.2.15 Participants with urine protein \geq 3.5 gram (g)/24 hour			
4.2.16 Administration of a live vaccine within 30 days prior to initiating study treatment Note: Seasonal influenza vaccines for injection are generally inactivated flu vaccines and are permitted; however, intranasal influenza vaccines (e.g., Flu-Mist) are live attenuated vaccines, and are not allowed. COVID-19 vaccines are allowed and encouraged			
4.2.17 Administration of any investigational agent within 4 weeks prior to initiating study treatment			
4.2.18 History of solid organ or allogeneic stem cell transplant			
4.2.19 Known intolerance to either of the study drugs (or any of the excipients)			
4.2.20 Known immunodeficiency, eg, human immunodeficiency virus (HIV) Note: HIV testing is not required for eligibility screening			
4.2.21 Known active hepatitis B or C			

	Yes	No	N/A
Note: hepatitis B and C testing is not required for eligibility screening			
4.2.22 Serious (ie, grade ≥ 3) uncontrolled infection			
4.2.23 Pregnancy or breastfeeding			
4.2.24 Diagnosis or treatment for another malignancy within 2 years prior to study registration, with the following exceptions: complete resection of basal cell carcinoma or squamous cell carcinoma of the skin, and any in situ malignancy.			
4.2.25 Medical, psychological, or social condition that, in the opinion of the investigator, may increase the patient's risk or limit the patient's adherence with study requirements			

5 STUDY ENTRY AND WITHDRAWAL PROCEDURES

5.1 Study Entry Procedures

5.1.1 Required Pre-Registration Screening Tests and Procedures

Refer to the study calendar in Section [12](#) for the screening tests and procedures that are required prior to registration and for the timing of these events relative to the start of treatment.

Screen failures are defined as patients who consent to participate in the clinical trial but are not subsequently registered in the study. Demographics and consent data for these patients are entered into OnCore.

5.1.2 Registration Process

After informed consent has been obtained, the following documents are submitted to the VCU MCC Coordinating Center [REDACTED] for study registration:

- Completed registration cover sheet or request form as provided by the coordinating center
- Attestation of patient eligibility
- Signed and dated consent form

The Coordinating Center will complete the registration process by assigning a study identification (ID) number and returning a Confirmation of Registration to the registering study team. Study treatment may not begin until the Confirmation of Registration

assigning a study ID number has been received from the registrar. The registering study team will enter the patient's initial enrollment data (eg, demographics, consent, eligibility, on-study, treatment assignment) into the OnCore database within 24 hours following study registration (before treatment begins).

5.2 Study Withdrawal

A patient may decide to withdraw from the study at any time. Patients must be withdrawn from the study when any of the following occurs:

- The patient has withdrawn consent for study treatment and study procedures.
- If, in the investigator's opinion, continuation of the study requirements would be harmful to the patient's well-being.
- The patient is lost to follow-up. (See Section [5.3](#))

The reason for withdrawal from the study and the date the patient was removed from the study must be documented in the source documents and OnCore database.

5.3 Lost to Follow-Up

A participant is identified as lost-to-follow-up (LTFU) if all of the following criteria are met:

- The last contact date for a participant has exceeded 2 consecutive years.
- Since the last contact date, documentation of at least 3 attempts to contact the participant by telephone and a certified letter to the last known address has either been returned or not answered within 7 days of confirmation that the letter was received or undeliverable.
- A Social Security Death Index (SSDI) search has been completed with negative results. If a participant is determined to be LTFU, the certified letter receipt will be filed in the participant's research record with a copy of the letter sent, a thorough explanation of the contact attempts will be documented in the participant's research record, and the participant's status will be changed/confirmed in OnCore.

6 STUDY TREATMENT

6.1 Baseline Tests and Procedures

Refer to the study calendar in Section [12](#) for requirements prior to initiation of therapy.

6.2 Investigational Agent Administration

Participants will receive pembrolizumab 200 mg administered by IV infusion on day 1 of each 21-day cycle plus lenvatinib 20 mg administered orally (PO) once daily (QD) during each 21-day cycle.

6.2.1 Premedications for Pembrolizumab

- Patients may be premedicated for nausea and vomiting. Choice of antiemetic is at the treating physician's discretion with the exception that steroids are NOT permitted for this purpose.
- Refer to [Table 1](#) for management of infusion reactions.

6.2.2 Administration of Pembrolizumab

Refer to Section [9.2.5](#) for preparation instructions.

- Administer reconstituted pembrolizumab in intravenous infusion bag of either 0.9% Sodium Chloride Injection or 5% Dextrose Injection.
- Administer infusion solution over 30 minutes through an IV line containing a sterile, non-pyrogenic, low-protein binding 0.2 micron to 5 micron in-line or add-on filter. (Do not co-administer other drugs through the same infusion line.)
- Every effort should be made to plan for administration as close to 30 minutes as possible. However, a window of -5 minutes and +10 minutes is permitted.

6.2.3 Pembrolizumab Infusion Reaction Treatment Guidelines

Severe infusion reactions have been reported in 2 (0.1%) of 1562 patients receiving pembrolizumab in clinical trials. Management of a pembrolizumab infusion reaction is outlined in [Table 1](#).

Table 1. Management of Pembrolizumab Infusion-related Reaction

Grade (NCI CTCAE v5.0)	Treatment	Premedication at Subsequent Dosing
Grade 1 Mild transient reaction; infusion interruption not indicated; intervention not indicated	Increase monitoring of vital signs as medically indicated until the patient is deemed medically stable in the opinion of the treating physician.	None
Grade 2 Therapy or infusion interruption indicated but responds promptly to symptomatic treatment (eg, antihistamines, NSAIDS, narcotics, IV fluids); prophylactic medications indicated for ≤ 24 hours	Stop infusion and monitor symptoms. Additional appropriate medical therapy may include but is not limited to: 
IV fluidsAntihistaminesNSAIDSAcetaminophenNarcotics Increase monitoring of vital signs as medically indicated until the patient is deemed medically stable in the opinion of the treating physician. If symptoms resolve within one hour of stopping drug infusion, the infusion may be restarted at 50% of the original infusion rate (e.g., from 100 mL/hour to 50 mL/hour). Otherwise dosing will be held until symptoms resolve; the patient should be premedicated for the next scheduled dose. Pembrolizumab should be permanently discontinued for patients who develop grade 2 toxicity despite adequate premedication.	Patient may be premedicated 1.5 hour (± 30 minutes) prior to infusion of pembrolizumab with: 
Diphenhydramine 50 mg po (or equivalent dose of antihistamine).Acetaminophen 500-1000 mg po (or equivalent dose of antipyretic).
Grade 3 Prolonged (ie, not rapidly responsive to symptomatic medication and/or brief interruption of infusion); recurrence of symptoms following initial improvement; hospitalization indicated for other clinical sequelae (eg, renal impairment, pulmonary infiltrates)	Stop infusion. Additional appropriate medical therapy may include but is not limited to: 
IV fluidsAntihistaminesNSAIDSAcetaminophenNarcoticsOxygenPressorsCorticosteroidsEpinephrine	No subsequent dosing
Grade 4 Life-threatening consequences; urgent intervention indicated; pressor or ventilatory support indicated	Increase monitoring of vital signs as medically indicated until the patient is deemed medically stable in the opinion of the treating physician. Hospitalization may be indicated. Permanently discontinue pembrolizumab.	

Note: Appropriate resuscitation equipment should be available in the room and a physician readily available during the period of drug administration.

6.3 General Concomitant Medication and Supportive Care Guidelines

- Patients should receive appropriate supportive care measures as deemed necessary by the treating physician and according to the current prescribing information for each agent.
- Patients may be premedicated for nausea and vomiting. Choice of antiemetic is at the treating physician's discretion with the exception that steroids are NOT permitted.
- Refer to [Table 1](#) for management of infusion reactions.

6.3.1 Supportive Care

- Patients should receive appropriate supportive care measures as deemed necessary by the treating physician
- Supportive care measures for the management of AEs with potential immunologic etiology, ie, irAEs, are outlined in [Appendix 2](#).

6.3.2 Prohibited Medications and Treatments

6.3.2.1 Cancer Treatment

Cancer treatment (e.g., chemotherapy, biological therapy, immunotherapy, radiation therapy) other than the treatment specified in the protocol for this study is not permitted during study treatment.

6.3.2.2 Other Medications

- Live vaccines (examples of live vaccines include, but are not limited to, the following: measles, mumps, rubella, varicella/zoster, yellow fever, rabies, BCG, and typhoid vaccine) are prohibited.
- Systemic glucocorticoids for any purpose other than to modulate symptoms from an event of suspected immunologic etiology are prohibited. Exception: Steroids equivalent to or less than an oral prednisone dose of 10 mg daily are permitted and steroids are allowed without limitation
- Any investigational agent not specified in the protocol for this study is not permitted.

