4.2.1 Endometrial leiomyosarcoma or endometrial stromal sarcoma			

		Yes	No	N/A
4.2.2	Unstable central nervous system (CNS) metastases			
4.2.3	Gastrointestinal malabsorption, gastrointestinal anastomosis, or any other condition that might affect the absorption of lenvatinib			
4.2.4	Pre-existing grade ≥ 3 gastrointestinal or non-gastrointestinal fistula			
4.2.5	Radiographic evidence of major blood vessel invasion/infiltration			
4.2.6	Clinically significant hemoptysis or tumor bleeding within 2 weeks prior to the first dose of study treatment			
4.2.7	History of congestive heart failure greater than New York Heart Association (NYHA) Class II, unstable angina, myocardial infarction, cerebrovascular accident, stroke, or cardiac arrhythmia associated with hemodynamic instability within 12 months of the first dose of study treatment			
4.2.8	Known history or evidence of interstitial lung disease or active, non-infectious pneumonitis			
4.2.9	Administration of or condition requiring administration of systemic steroid therapy or any other form of immunosuppressive therapy within 7 days prior to initiating study treatment Exception: Patients with conditions that can be managed with steroids equivalent to or less than an oral prednisone dose of 10 mg daily are not excluded from the study			
4.2.10	Active autoimmune disease (with the exception of psoriasis) that has required systemic treatment in the past 2 years (ie, with use of disease-modifying agents, corticosteroids, or immunosuppressive drugs) or a documented history of clinically severe autoimmune disease or a syndrome that requires systemic steroids or immunosuppressive agents Note: Patients with the conditions or medical history listed below are not excluded from the study. 
• Vitiligo• Resolved childhood asthma/atopy• Requirement for intermittent use of bronchodilators or local steroid injections or topical steroids			

	Yes	No	N/A

 • Hypothyroidism stable on hormone replacement • Sjogren's Syndrome 			
4.2.11 Has received >2 prior systemic chemotherapy regimen (other than adjuvant or neoadjuvant) for endometrial cancer; participants may receive up to 2 regimens of platinum-based chemotherapy in total, as long as one is given in the neoadjuvant or adjuvant treatment setting			

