13.2 Sample Size/Accrual Rates

As the goal of this proposal is to estimate ORR, we will not formally power for hypothesis testing. With 100 subjects (and conservatively assuming a 0.5 ORR for maximum variability), we would be able to estimate the ORR with a margin of error of ± 0.1 .

This study is expected to be open to accrual at a total of 10 sites across the US within 24 months of its initial approval at the coordinating site, VCU Massey Cancer Center. Each site is anticipated to accrue an average of 1 patient every 2 to 3 months. The total period of study recruitment is therefore anticipated to occur over a period of 25 to 42 months, with recruitment complete by July 1, 2025.

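### Section 6.3.2.2 contradicts itself on steroids: its last clause, which carries no qualifier, removes the prohibition and the 10 mg/day limit in the same bullet

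*Combined protocol and SAP*

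**What the plan says.** The rule is one bullet in 6.3.2.2, under the heading "6.3.2 Prohibited Medications and Treatments". It opens with a prohibition that has a built-in exemption: "Systemic glucocorticoids for any purpose other than to modulate symptoms from an event of suspected immunologic etiology are prohibited". An exception follows: "Steroids equivalent to or less than an oral prednisone dose of 10 mg daily are permitted and steroids are allowed without limitation".

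Steroids are also addressed in these places:

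- **6.2.1**, on antiemetic premedication for pembrolizumab: "steroids are NOT permitted for this purpose".
- **6.3**, repeating the antiemetic rule: "with the exception that steroids are NOT permitted".
- **4.2.9**, the exclusion for systemic steroid or other immunosuppressive therapy within 7 days before treatment, with its own exception for patients managed on "steroids equivalent to or less than an oral prednisone dose of 10 mg daily are not excluded from the study".
- **4.2.10**, whose note lists among the circumstances that do not exclude a patient: "Requirement for intermittent use of bronchodilators or local steroid injections or topical steroids".
- **Table 1, 9.2.10 and Appendix 2**, which provide for corticosteroids in managing severe infusion reactions and immune-related events.

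**The concern.** The bullet makes three statements that cannot all operate as printed: a prohibition, a dose-limited exception to it, and an allowance with no limit. This is an operative rule in the list of prohibited medications, so sites and monitors must apply it.

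What is at stake is consistent conduct. The trial is single-arm (3.1), its primary endpoint is the objective response rate at 24 weeks (3.2), and one of its two drugs acts through the immune system. With no concurrent control group, there is no comparison arm in which uneven steroid use could balance out. Concurrent medications are collected at baseline, every cycle and end of therapy (Section 12), so steroid use will be visible. Visibility does not settle classification, however. The compliance monitoring and auditing in 14.1.1 need a rule to check records against, and for one class of use this bullet does not supply one.

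**Working it through.** No arithmetic applies. No figure in the plan depends on this rule, and 13.2 says of the design that "we will not formally power for hypothesis testing". The check is a side-by-side reading.

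**Step 1: what each part of the bullet does.**

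- Part (a) prohibits systemic glucocorticoids, except to treat a suspected immune-mediated event.
- Part (b) takes daily doses up to 10 mg oral prednisone equivalent out of the prohibition.
- Part (c) allows steroids with no limit and does not say which steroids.

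If (c) means all steroids, (b) has no work to do and nothing is left of (a). If (a) and (b) are to have effect, (c) must cover something narrower than its words say.

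**Step 2: is a restriction intended?** Yes. The bullet sits in a list of prohibited treatments. Criterion 4.2.9 applies the same 10 mg/day threshold at entry. Sections 6.2.1 and 6.3 both bar steroids as antiemetics. The literal reading of (c) is therefore unlikely to be what was meant, but it is what is printed.

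**Step 3: which uses change class depending on how (c) is read?**

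| Steroid use during treatment | If (a) and (b) govern | If (c) is read as printed | Ambiguous? |
|---|---|---|---|
| For a suspected immune-mediated event | Permitted | Permitted | No |
| Systemic, up to 10 mg/day, not antiemetic | Permitted | Permitted | No |
| Topical or local | Outside (a), which covers systemic use only | Permitted | No |
| As an antiemetic | Barred by 6.2.1 and 6.3 | General wording of (c) conflicts, but the purpose-specific bans remain in force | Deviation still identifiable |
| Systemic, above 10 mg/day, neither antiemetic nor for an immune-related event | Prohibited | Permitted | **Yes** |

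Corticosteroids for severe infusion reactions have their own provision in Table 1 and do not depend on part (c).

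**Step 4: does any other place resolve the last row?** The note to 4.2.10 shows that the protocol can distinguish local and topical steroids from systemic ones. It is an eligibility note, however, and 6.3.2.2 neither repeats nor cites it. The other steroid statements (6.2.1, 6.3, 7.4, 9.2.10, Appendix 2) concern antiemetics or the management of immune-related events. None says what part (c) covers.

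**The case against.** The strongest reply is that this is a lost word and not a flaw in the plan. The bullet ends without a full stop, unlike its two neighbours, and the second mention of steroids reads as if an adjective once stood before it. The public copy has lost text elsewhere: the contents list 11.2 to 11.5, but the body goes from 11.1 to a redacted 11.4.1 and then to 11.6. On this view the missing word is something like topical or local, as in 4.2.10, and the prohibition and limit are intact.

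The reply is plausible, and part of it stands: loss of a word in the public copy cannot be excluded. But the sentence shows no redaction mark or visible gap, and the non-systemic reading is stated nowhere. Nor is it the only candidate, since the missing qualifier could concern route, formulation or purpose, and sites could fill the gap differently. A probable slip in an operative rule still needs correcting.

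A second reply is that the practical reach is small. That also stands. Immune-related events can be treated with corticosteroids under any reading, antiemetic use stays barred by rules specific to that purpose, and all use is recorded.

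A reader might go further than the text allows in three ways:

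- **That the protocol places no restriction on steroids.** It does: 4.2.9, 6.2.1 and 6.3 remain in place.
- **That every patient is affected.** Only patients given the one class of use marked in the table are affected, and the documents do not say how many that would be.
- **That the response rate will be biased.** Nothing in the documents links this clause to a change in response. Section 9.2.9 reports no relationship between prolonged systemic corticosteroids and pembrolizumab exposure. That is a pharmacokinetic statement, so it neither supports nor rules out an effect on response.

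**Conclusion.** Wrong as written: an internal contradiction in an operative rule. As printed, the last clause of the 6.3.2.2 exception removes the 10 mg/day limit and the prohibition. Up to 10 sites treating up to 100 patients therefore have no usable standard for one class of use: systemic, above 10 mg/day, not antiemetic and not for an immune-related event. How often such use will occur, and whether it would move the objective response rate, cannot be derived from the documents.

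The conclusion assumes that the public text reproduces the sentence in the approved protocol. If the approved text contains a qualifier that the public copy lost, the point reduces to a copy error. No view is taken here on which steroid rule is clinically right.

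**What to change.** First check the sentence against the approved source document. If a qualifier is present there, correct the public copy. If not, amend the exception so that it states which steroids the unlimited clause covers, and reconcile it with the prohibition and the 10 mg exception in the same bullet and with 4.2.9, 6.2.1 and 6.3. The clinical team decides the content.

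The cost is a one-sentence amendment and a notice to sites. Sample size, endpoints, visit schedule and data collection do not change. Because concurrent medications are already recorded, steroid use to date can be classified against the clarified rule without new data.

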6.4 Duration of Therapy

Study treatment will be administered per [schema](#) unless one of the following occurs (also see study withdrawal criteria in Section [5.2](#)):

- AE that requires discontinuation of study treatment (see Section [8](#))
- Pregnancy
- Determination by the investigator that discontinuation is in the patient's best medical interest

- Patient decision to discontinue study treatment
- Withdrawal of study sponsor support

The reason for discontinuation of study treatment must be documented in the source documents and in the OnCore database.

6.5 Duration of Follow-Up

6.5.1 Initial AE Evaluation Period after Discontinuation of Treatment

Patients who discontinue treatment **for any reason other than death or their choice to withdraw from all study follow-up** remain on study in follow-up status for an initial 30-day AE evaluation period following the last dose of study treatment. This 30-day post-treatment follow-up period is meant to capture resolution or stabilization of ongoing treatment-related AEs or evolution of new treatment-related AEs.

The initial AE follow-up period may be extended if new or worsening treatment-related AEs require longer observation. Similarly, the initial AE follow-up period may end early in the event of death, patient request to withdraw from follow-up, or initiation of new anticancer therapy.

6.5.2 Ongoing Follow-up

Patients who discontinue treatment with ongoing SD, PR, or CR (see Section 10) remain in follow-up status for PFS by reported clinical status every 3 months until one of the following occurs: disease progression, relapse, or death.

All patients will be followed for OS status every 3 months, until death or off-study.

The primary reason(s) for a patient's discontinuation from study treatment and from follow-up status are to be recorded in the source documents and the OnCore database.

6.6 Study Pocket Card for Patients

A pocket card identifying the name of the study, the names of the study medications, and contact information including the study team and a 24-hour on-call study physician will be provided to each patient. The purpose of this card is to facilitate communication between the study team and the patient's health care providers not involved with the study. Patients will be encouraged to carry the card with them at all times and to show it to their health care providers so that potential interactions with the study medications can be identified before initiating new medications.

6.7 Monitoring Patient Adherence

Patients will be instructed to record their lenvatinib doses in the drug diary that will be provided.

Adherence will be assessed at time points per [Study Calendar](#). Patient reports of self-administration, review of the study drug diary, and lenvatinib pill counts will be used to

assess the patient's adherence with the oral study treatment regimen. Adherence is defined as taking $\geq 80\%$ of planned lenvatinib doses in a cycle. Doses omitted due to AE management will not count towards nonadherence. Patients who are not adherent will be re-instructed.

